Sickle cell leg ulcers (SCLUs) are a challenging chronic wound type whose sufferers could benefit from a more economical, less painful, dressing option.^{8,9} Only one of the studies involving occlusive plastic improvised dressings took place in a tropical environment, and this study tested a sterile drape placed in an operating theater on surgical wounds (donor sites).⁵⁸ Although theoretically autolytic debridement should keep wounds dressed with plastic bags clean, in practice there are concerns that wound infections could be problematic, because tropical climates are known to promote increased microbial growth.¹⁹ Therefore, it is prudent to test the plastic bag dressing protocol under the guidance of health care professionals, where sufficient numbers of patients can be enrolled at a single site to answer the study questions definitively.

UHWI (the University Hospital of the West Indies) provides a rare intersection of sufficient research expertise to obtain accurate data, and a large number of SCLU patients living in a true tropical climate (air conditioning is not pervasive), allowing for partial testing of the ecological validity of improvised dressings. Validating the safety and effectiveness of affordable dressing materials would vastly improve treatment outcomes by winnowing out harmful self-care choices and supporting the beneficial choices. It would also empower patients, their families and lay health care providers by enabling them to implement effective treatments as first aid, prior to their arrival at an outpatient clinic or hospital.

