(3) Is the *improvised dressing* culturally acceptable to health care providers, patients, and families for managing SCLUs in Jamaica?

The expected study outcome is improvised dressing superior effectiveness and quality of life, when compared with usual practice, without increased safety and acceptability issues.^{13,59,60,62} The improvised dressing is likely to be the least expensive choice, with the added benefit of being available as first aid treatment throughout Jamaica. The advanced dressing is likely to be more expensive with respect to materials costs, although fewer dressing changes are anticipated and pain medication expenses are likely to be reduced. Based upon the review of the literature, no serious infections or other safety issues are anticipated for any group. However, to ensure that complications are not overlooked, in addition to the onsite researchers' vigilance, weekly wound photos will be assessed for complications (signs of infection, wound deterioration, or clinically relevant maceration) by two off-site blinded wound experts, Drs. [name] and [name].

Definitions:

Sickle cell leg ulcer – a wound in a HbSS or HbS β^0 positive patient, open greater than one month,⁷ below the level of the knee excluding the plantar surface of the foot.

Closed wound -100% epithelialized with no discernible scab or exudate production (paper napkin remains dry when lightly pressed against area, and no recurrence in the subsequent two weeks)

Safe – infection and other complications (healing-impairing maceration, keloid, and contracture rates) not statistically significantly higher than usual practice, with no major adverse events attributable to the method

Effective – ulcer closure rates or ulcer surface area reduction rates not statistically significantly lower than usual practice

Acceptable – average acceptability scores of 4 or higher on a 1-5 scale

3. Methods and Materials

a. Study design

This study will be a targeted-blinded (the off-site wound experts and the local physicians verifying wound closure and/or complications will be blinded to the randomization group), randomized controlled trial with three arms: (1) usual practice (negative control), (2) the improvised dressing, and (3) the advanced dressing (positive control). The expected outcome is improvised and advanced dressing superiority.

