- 2. Age of open wound prior to entrance into study (in weeks, patient/family report)
- 3. Previous ulcer treatments (if any)
- 4. Education level (in years)
- 5. Smoking or any use of nicotine (yes/no in past week)^{84,85}
- 6. Mid-arm circumference (a surrogate for nutritional status) 91,92
- 7. Initial area of SCLU in cm^2 (see methods for multiple adjacent SCLUs)
- 8. Initial depth of SCLU at deepest point, in cm
- 9. Anatomic location of SCLU
- 10. ASCQ-Me baseline scores (all measures see appendices)
- 11. Social isolation (lives alone, without nearby support)⁸⁶
- e. Inclusion and exclusion criteria

Inclusion Criteria:

- > Diagnosed with HbSS or HbS β^0 sickle cell disease
- > Ages 13 70 years at study initiation (able to comprehend and give consent)⁸²
- > Males and females, pregnancy is not an issue
- > Open wound below the knee, not including the plantar surface of the foot
- > Wound open for longer than one month (defined as a chronic SCLU)
- > Traumatic, spontaneous, or recurrent SCLU (all etiologies)

Exclusion Criteria:

- > Patient younger than 13 years of age at study initiation
- > Patient older than 70 years of age at study initiation
- Wound open for less than one month by conclusion of study enrollment period (acute wounds could be traumatic wounds unrelated to sickle cell diagnosis)
- ➤ Diagnosis of cancer, hypertension, or chronic renal failure⁸²
- ➤ Diabetes (will screen for undiagnosed diabetes)⁸²
- Active wound infection (evidenced by clinical signs of malodor, dark-colored or thick drainage, or significantly increased warmth at the periwound) which is not resolved by the conclusion of the study enrollment period
- Osteomyelitis (if osteomyelitis is suspected, an ESR will be drawn; > 70mm/h with high platelet levels and low serum albumin warrants a bone biopsy)^{93,94}

> Hydroxyurea use (may be a confound because it reduces inflammation and negates much of the pathology of SSD – may choose to abstain for the study)^{7,95}

f. Sampling

- i. All eligible participants who consent to the study will be included. Participants will be randomized into one of the three groups immediately after the initial cleansing/debridement of their SCLU by the nurse using an electronic random number generator (an app). Waiting until the study dressing is to be applied to generate the random number will provide allocation concealment.

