Patients (and adult relatives of eligible patients under the age of 18) will have the study explained to them by one of the members of the UHWI surgical team. Questions will be addressed thoroughly. Families will be assured that if they choose not to participate in the study, the SCLU will be managed with usual practice. The patient (and a decision-maker of the family, in the case of a minor) must sign the consent for the patient to be enrolled in the study.

Immediately after consent is obtained, the study tools (Patient Data Collection sheet, Faces Pain Scale – Revised (FPS-R), ASCQ-Me, and Wound QoL) will be explained to the patient and family. Baseline persistent pain will be assessed using the Faces Pain Scale – Revised (FPS-R).

All of the initial independent variable data will be handwritten onto the patient's individual Study Data Collection Form upon enrollment in the study. The largest SCLU upon initial presentation is the study wound. All SCLUs will be measured for the first four weekly visits to UHWI. If two or more SCLUs in close proximity join during the first four weeks, the sum of the initial areas will be the initial wound size.

The SCLU(s) will be measured initially by placing two pieces of clear plastic on top of one another and tracing the wound edges. The plastic that came in contact with the wound(s) will be discarded and the plastic with the markings on it will be added to the patient's documentation so that the patient can be shown if the SCLU is becoming smaller at subsequent dressing changes. SCLU area will be measured in cm² electronically from a photo, using software such as HealthEPix or WoundMatrix.

Patients (with the support of their families) will be taught to evaluate and document persistent and dressing change pain, pain medication doses taken, time spent and supplies used at dressing changes, their activity, and their use of compression on a checklist-style Study Continuation Form daily. They will either provide the research team with their weekly summary and wound photo via WhatsApp, or they will attend the clinic weekly so that the research team can obtain this data. Two encrypted USB drives containing the data, including wound photographs, will be updated weekly on an alternating schedule and stored in a securely locked file in the UHWI surgical clinic dressing area, along with the paper study documentation.

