Study patients will be randomized into groups 1, 2, or 3 immediately AFTER initial thorough wound cleansing/debriding by the nurse or physician. Randomization will be accomplished using an electronic random number generator (an app).

After a member of the UHWI surgical team performs the initial cleansing/debriding, the control group (1) will have their ulcer dressed as usually done at UHWI. Wounds are dressed with saline-soaked gauze, covered with dry gauze. One wrap of stretch gauze will hold the dressing in place. Patients will clean the wound by vigorously wiping with gauze soaked in homemade normal saline (1 tsp salt/500ml water bottle), center to edges, at each dressing change, unless already very clean. Clean wounds will simply be irrigated with normal saline at each dressing change. Patients experienced with using papaya for debridement of their ulcers may apply it only to the open wound, avoiding contact with the periwound, to remove slough or eschar. If patients observe green exudate, they are permitted to add one teaspoon of vinegar to their bottle of saline. Dressings in group (1) will be changed daily. The dressings will be soaked off if they become adherent.

After initial cleansing/debriding, patients in the improvised dressing group (2) will then have a thin layer zinc oxide paste applied to the dried periwound, carefully avoiding the open wound.⁹⁷ A piece of a clean new plastic bag (food-grade World Star 1 mil LD bags, or the equivalent, purchased from the Papine Market across John Golding Road from the University of the West Indies), cut slightly larger than the ulcer will be gently conformed to the moist wound contours and sealed onto the zinc oxide paste. The bag will be fenestrated with a small slit using a number 11 scalpel or clean scissors prior to placing it on the ulcer in order to allow excess fluid to escape. The edges of the slit will be approximated. Clean gauze will be placed lightly over the slit to capture escaping fluid. One wrap of stretch gauze will hold the dressing in place. Patients will be instructed to change the dressings daily, irrigating with normal saline at each dressing change.⁶

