After initial cleansing/debriding, the advanced dressing group (3) will have a cut piece of a 4"x24" standard (pink) PMD roll large enough to extend at least 0.5 cm beyond all open and closed (inflamed or damaged) wound edges applied as per the Instructions for Use (the periwound is blotted dry, but the wound bed remains moist from the final saline rinse). One wrap of stretch gauze will hold the PMD dressing in place. The approximate open wound edges will be marked on the dressing backing. As per the manufacturer's instructions for use, patients will change the dressings when saturation reaches any of the wound edges, as indicated by a change in color on the backing of the dressing, visible through the stretch gauze. Routine rinsing will not be performed; the wounds will be rinsed at dressing changes only if visible loose debris is present.

All study patients will receive education about their illness and pain medication prescriptions per usual protocol. Patients are advised to use a compression wrap whenever their foot is dependent, as often as they are able to tolerate it. They will each be given a zipper-bag to contain and keep their wound management supplies clean.

Patients will be required to come to the UHWI surgical clinic dressing area in person weekly during the initial 4 weeks of study enrollment so that wound photos can be taken and the data for the ten dependent variables that are to be assessed weekly can be obtained. If their SCLU is clean without evidence of complications, patients/families who demonstrate the ability to take adequate pictures of their study SCLU with their mobile devices may instead send photos of their wound and their data collection sheets to the research team via end-to-end encrypted text messaging system (WhatsApp). All patients must agree to come to UHWI at least once per month to avoid being withdrawn from the study. Appointment times will include evenings and Saturdays to accommodate the schedules of students and employed patients.

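### After week 4 most infection checks can be photo-only, and the infection signs the plan names are mostly invisible in a photo and not listed for the daily patient form, so under-detection makes 'safe' easier to conclude

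*Combined protocol and SAP*

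**What the plan says.** Section 1b gives infection as the reason for testing the plastic dressing under supervision: "in practice there are concerns that wound infections could be problematic, because tropical climates are known to promote increased microbial growth". Section 2 puts infection first in its definition of 'safe', which is met if complication rates are not statistically significantly above usual practice and no major adverse event is attributable to the method. Section 3d makes complication rates, including infection, a weekly outcome (dependent variable 9) but gives no criteria for diagnosing infection on study. The only signs named are those for excluding an actively infected wound at entry (section 3e): "clinical signs of malodor, dark-colored or thick drainage, or significantly increased warmth at the periwound".

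On surveillance, section 2 says that, in addition to the vigilance of on-site staff, "weekly wound photos will be assessed for complications (signs of infection, wound deterioration, or clinically relevant maceration") by two blinded off-site experts. Section 3h requires attendance "in person weekly during the initial 4 weeks of study enrollment". After that, "If their SCLU is clean without evidence of complications" and the patient or family can take adequate pictures, they "may instead send photos of their wound and their data collection sheets to the research team"; a visit is then required at least monthly. The burden statement in section 4 also describes a monthly in-person visit.

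The daily Study Continuation Form is described in section 3h as covering persistent and dressing-change pain, "pain medication doses taken, time spent and supplies used at dressing changes, their activity, and their use of compression". A physician blinded to group examines the patient when the experts, or anyone else in the study, raise a concern.

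For group 1 only, section 3h adds: "If patients observe green exudate, they are permitted to add one teaspoon of vinegar to their bottle of saline". It does not say whether this is to be reported.

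**The concern.** In the remote weeks no staff member sees, smells or touches the wound. The photo review, presented as a supplement to on-site vigilance, becomes the main check on the hazard the trial is meant to assess. It cannot show two of the three named signs, and the described content of the daily form does not fill the gap. The blinded examination starts only when somebody raises a concern, and section 3h ties no patient-recorded sign to that step.

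Two things are at stake. For patients, an infection may be recognised late. For the analysis, detection that is incomplete to the same degree in every arm shrinks the recorded difference, and a rule that declares safety on non-significance is easier to pass when cases are missed.

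**Working it through.** **1. Exposure to photo-only checks.** Inputs from section 3h: weekly visits in weeks 1–4, at least one visit a month afterwards, 12 weeks of follow-up. Assume the monthly visits fall at weeks 8 and 12 and the ulcer stays open.
- Checks after week 4: 12 − 4 = 8.
- In person: 2 (weeks 8 and 12).
- Photo-only: 8 − 2 = 6 (weeks 5–7 and 9–11), at most 3 in a row; 6 of 12 over the whole follow-up.

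**2. What each channel can show.**

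| Sign (section 3e) | Visible in a photo? | Listed for the daily form (section 3h)? |
|---|---|---|
| Malodor | No | No |
| Dark or thick drainage | Colour perhaps; thickness poorly | No |
| Periwound warmth | No | No |

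Two of the three signs are invisible and the third is partly visible.

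**3. Sample size.** Section 3f: 90 participants, 25% dropout, up to 120 recruited. 90 / (1 − 0.25) = 120, which reproduces. That gives 30 per arm after dropout and 40 as recruited. The 30 per arm cannot be reproduced from an infection rate, because the plan gives none.

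**4. Effect on the 'safe' rule.** Assumptions: true infection rates p₁ (usual practice) and p₂ (improvised dressing); the same detection fraction d in both arms, so the recorded rates are d·p₁ and d·p₂; Fisher's exact test, two-sided 0.05 (the plan names no test for complication rates; 0.05 is taken from its 95% intervals). The chance of flagging the excess is the sum of Bin(i; n, d·p₁) × Bin(j; n, d·p₂) over all counts i < j with Fisher p < 0.05. For 10% vs 30%, the recorded rates are 7.5% vs 22.5% at d = 0.75 and 5% vs 15% at d = 0.5.

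| True rates | n per arm | d = 1 | d = 0.75 | d = 0.5 |
|---|---|---|---|---|
| 10% vs 30% | 30 | 37% | 23% | 9% |
| 10% vs 30% | 40 | 53% | 37% | 18% |
| 10% vs 40% | 30 | 71% | 49% | 24% |
| 5% vs 20% | 30 | 24% | 12% | 4% |

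A normal approximation for 10% vs 30% at 30 per arm gives 49%, 37% and 25%: higher, with the same pattern.

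**5. How few cases matter.** At 30 per arm, the smallest significant splits are 0 vs 6, 1 vs 8 and 2 vs 9. One missed case in group 2 turns 2 vs 9 (p = 0.042) into 2 vs 8 (p = 0.080), and the excess is no longer flagged.

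**6. Placing the detection fractions.** At most half of all weekly checks are photo-only (6 of 12). If onsets are spread evenly and every infection arising in an in-person week is found, d = 0.5 requires every photo-week onset to be missed for good: 0.5 + 0.5 × 0 = 0.5. d = 0.75 requires half of them to be missed: 0.5 + 0.5 × 0.5 = 0.75. So 0.5 is close to the worst case.

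**The case against.** The other side has real points.

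- **Safeguards exist.** Photo follow-up is only for clean ulcers, visits continue monthly, pain and pain medication are recorded daily, and anyone in the study may raise a concern. This stands. A persistent infection is likely to be found late, not never. A reader might infer that infections after week 4 go undetected; the documents do not support that. What remains is delay, and loss of infections that arise and resolve between visits.
- **The form was not seen.** The tools are in appendices that were not supplied. The data sheets sent in place of a visit, or the Wound QoL items, may cover odour or drainage. It cannot be said that the form omits these signs, only that its description in section 3h does not list them. Even if an item exists, no patient answer is linked to the physician evaluation.
- **The signs are entry criteria.** True, and the on-study trigger, signs of possible infection, is worded more broadly. But no other signs are named, so the experts have no stated criteria.
- **Drainage might be photographed.** It might. Section 3h does not say whether photos are taken before or after cleansing, so nothing can be built on the wound having been cleaned first.
- **The safety test is weak anyway.** Yes. With 40 per arm, 4 vs 8 infections is non-significant with full detection (Fisher p = 0.35), as is 2 vs 4 (p = 0.68). Missed cases worsen a weakness that has other causes.
- **The vinegar provision.** A reader might infer that it helps the improvised dressing to look safe. The direction is the reverse: if it hid infections in group 1 alone, the control rate would fall and 'safe' would be harder to conclude. Nor is it shown to go unrecorded, since supplies used are tallied, and green exudate is not among the section 3e signs. It is a gap in recording, not evidence of bias towards safety.

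**Conclusion.** The concern holds in a limited form. For a patient on the minimum schedule who stays 12 weeks, 6 of the 8 checks after week 4 can be photo-only, while two of the three named infection signs cannot be photographed and none is listed for the daily form as described. Because 'safe' is a non-significance rule, equal under-detection across arms makes that verdict easier to reach. In the 10% vs 30% illustration, losing a quarter of cases lowers the chance of flagging the excess from 37% to 23% at 30 per arm, or from 53% to 37% at 40; losing half, close to the worst case, gives 9% or 18%.

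The infection rates, the detection fractions, their equality across arms and the choice of test are assumptions. The documents do not show how often infections would be missed. The change is worth making because it improves both patient safety and ascertainment at little cost.

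**What to change.** 1. State in section 3d or 3h that the section 3e signs also serve as on-study infection signs in all three groups.
2. Add yes/no items for odour, dark or thick drainage, and periwound warmth to the Study Continuation Form, or confirm that it already has them.
3. Send these answers, without items that identify the group, to the blinded experts with each weekly photo, and say that a new or worsening sign counts as an expressed concern under the evaluation already described in section 3h.
4. Record any use of vinegar, and reconcile the group 1 green-exudate provision with the referral text in section 3h so that it is clear how such exudate is reported. No treatment rule is proposed.

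Cost: three tick boxes and a vinegar entry on an existing daily form, plus a few sentences of text. There will be some extra referrals. They may differ by arm because patients are unblinded (section 5) and drainage may differ between dressings. That risk is limited, not removed, because the physician's evaluation is blinded.

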- Based upon previous studies and the Central Limit Theorem, an estimated 90 participants (~30 per group) may be required for the differences between groups to reach statistical significance.^{12,23,88,89,96} Up to 120 patients will be recruited to allow for a 25% dropout rate. Based upon the literature review, pain, costs, wound size, and quality of life are expected to be significantly improved using the improvised dressings. However, because SCLUs are, historically, very slow to heal and often enlarge, complete wound closure is not an expected outcome for all patients.

g. Procedures for recruitment and consent

The study will be advertised using free community information channels such as church bulletins and radio outlets. Social media sites such as the CAIHR Facebook page will also be employed. Qualifying patients in the SCU database from up to two years prior to the study initiation will be called by the UHWI surgical team, alerting them to the dates for registering to participate. Flyers will be posted at the SCU in advance. Consent will be obtained by a member of the research team while the potential participant is waiting to be seen for wound care.

h. Data collection

The site for this study is the surgical clinic dressing area at the University Hospital of the West Indies (UHWI), Mona, Jamaica. The adjacent Sickle Cell Unit (SCU) will refer any SCLU patients to UHWI during the study period. UHWI is consistently well staffed with competent Jamaican health professionals. The UHWI surgical team will lead the study. Relatively few Jamaicans live or work in air-conditioned environments, ^[data in appendices] allowing the results from this out-patient population to translate to less developed tropical countries.

To ensure consistency, members of the research team will practice until they can demonstrate competency with all three dressing change procedures and with explaining the study forms prior to study patient recruitment.

Enrollment in the study will begin within two weeks of the day the Principal Investigator arrives at the Mona campus and will close 60 days later, or when a maximum of 120 patients have enrolled. All sickle cell positive patients presenting to UHWI with lower leg ulcers during the enrollment period will be screened for eligibility to enter the study. Each patient's data will be recorded for a total of 12 weeks, or until their SCLU has been closed for 2 weeks, whichever comes first.

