Weekly, de-identified photographs will be sent by the Principal Investigator to be viewed by two blinded wound experts ([name] and [name]) off site. If the blinded experts, or anyone else involved in the study, expresses concern that a patient is exhibiting signs of possible infection, maceration that is delaying healing, or wound deterioration, a physician at UHWI or the SCU who is not otherwise involved in the study will be asked to evaluate that patient. The patient's dressings will be removed prior to this evaluation so that their treatment group will not be revealed to the physician (the evaluation by the physician is thus blinded to treatment group). If the physician determines that the patient's condition has not improved with the prescribed treatments (e.g., antibiotics), the patient will be withdrawn from the study. Any

patient who transitions out of the group to which they were randomized for any reason will receive usual treatment for their ulcer for the remainder of their 12 week study period.

When the treatment personnel at UHWI or the blinded remote observers state that the patient's wound appears to be closed, a physician at UHWI or the SCU who is not otherwise involved in the study will be asked to evaluate that patient. The patient's dressings will be removed prior to this evaluation so that their treatment group will not be revealed to the physician. Wound closure is defined as 100% epithelialized with no discernible scab or exudate production (a paper napkin blotting the area remains dry). Patients will be reassessed two weeks later to verify that the wound was truly closed and did not immediately recur.

Patients who are diagnosed with wound closure or have completed the 12 week study period will be taken aside privately and asked to rate the acceptability of their treatment using a 5 point Likert Scale. A family decision-maker will also be privately asked to rate the acceptability of the treatment. One of the research team members will enter this basic acceptability data for the patient and the family on the patient's Data Collection Tool. At that point, the patient will graduate from the study. However, patients and families will be instructed to return to UHWI for follow-up if a complication or recurrence develops. Any delayed complications (e.g., recurrence within 3 months) will be recorded on the patient's Data Collection Tool by the nurse or physician to whom the patient reports it.

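### Hydroxyurea users from age 13 may qualify by stopping the drug for up to 12 weeks, and the supplied text requires no treating-clinician agreement, time off drug or restart rule

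*Combined protocol and SAP*

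**What the plan says.** Hydroxyurea appears once in the supplied text, as the last exclusion criterion in section 3e. The reason given is that it "may be a confound because it reduces inflammation and negates much of the pathology of SSD". The same line then says that a user "may choose to abstain for the study". Eligible ages are 13 to 70.

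Other sections bear on what abstaining would involve:

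- **Duration (3h, Data collection).** Each patient's "data will be recorded for a total of 12 weeks, or until their SCLU has been closed for 2 weeks, whichever comes first".
- **Consent (3g).** "Consent will be obtained by a member of the research team while the potential participant is waiting to be seen for wound care". Section 4 requires a parent or guardian's signature for those under 18.
- **Randomisation (3f).** "Participants will be randomized into one of the three groups immediately after the initial cleansing/debridement of their SCLU".
- **Physician review (3h).** A physician not otherwise involved in the study sees a patient thought to be "exhibiting signs of possible infection, maceration that is delaying healing, or wound deterioration". Anyone involved in the study may raise this, and the patient is withdrawn if treatment does not help.
- **Definition of safe (section 2).** Wound complication rates not significantly higher than usual practice, "with no major adverse events attributable to the method".
- **Contact.** The Sickle Cell Unit identifies past ulcer patients (3b), refers patients and may supply the reviewing physician (3h). Patients attend weekly for four weeks and then at least monthly (3h).
- **Variables (3d).** None of the 11 independent or 14 dependent variables names hydroxyurea.

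**The concern.** The plan describes hydroxyurea as acting against the disease and then offers a route into the trial that depends on giving it up. The trial concerns dressings, so stopping a systemic drug is not part of any treatment under test. Entry also brings free dressings and wound care (section 4) and phone cards (3h), so abstaining carries some incentive. Section 4 itself describes the 13 to 18 age group as especially vulnerable.

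A patient might stop without the knowledge of the clinician managing the sickle cell disease, and become unwell in a way that no stated trigger would pick up. With no rule on resuming, the patient might also believe that restarting means leaving the study. A lesser, statistical matter is that the trial might be unable to report who stopped, when, or who resumed, by arm.

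**Working it through.** The point turns mainly on setting the sections side by side.

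**1. How long.** Abstaining for the study means up to 12 weeks, less if the ulcer closes early (3h). No time off drug before randomisation is set, so a patient could stop on the day of entry or some time before. Total time off could therefore exceed 12 weeks. A same-day stop would also leave unclear whether the confounding cited in 3e had been removed.

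**2. Who agrees.** The described sequence is consent by a research team member in the waiting area (3g), cleansing or debridement, then immediate randomisation (3f). No step asks the treating sickle cell clinician to agree to an interruption. The Sickle Cell Unit's stated tasks are identifying, referring and possibly reviewing; none is approval of stopping.

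**3. What would be noticed.** Regular visits provide contact. Pain, pain medication and the sickle cell quality-of-life forms are collected weekly (3d), but no text links them to a review of the decision to stop. The triggers in 3h concern the wound. The section 2 definition counts a major adverse event only if it is due to the dressing method. As worded, systemic harm from stopping hydroxyurea falls outside both.

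**4. What would be recorded.** The item on previous ulcer treatments might catch some past use. The medication items in 3d and 3h name pain medication only. The data collection form itself was not available, so this step is weaker than the first three.

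**5. Exposure under assumed shares.** The formula is participants × share abstaining × 12 weeks. The 90 and 120 come from 3f (90 / (1 − 0.25) = 120, which reproduces the plan's recruitment maximum). The shares are assumptions.

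| Share abstaining | 90 participants | 120 participants |
|---|---|---|
| 0% | 0 | 0 |
| 5% | 4.5 patients, up to 54 patient-weeks | 6 patients, up to 72 |
| 10% | 9 patients, up to 108 | 12 patients, up to 144 |
| 20% | 18 patients, up to 216 | 24 patients, up to 288 |

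**6. Why no power figure is offered.** The plan states no power, effect size or standard deviation, and nothing on the effect of withdrawal. To show how far the answer depends on assumptions, take a two-sample t-test, two-sided 5%, 30 per arm, with 80% power as a reference (detectable effect 0.736 SD). Keeping a share p of abstainers whose outcome shifts by w SD multiplies the variance by 1 + w²p(1 − p).

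| Scenario | p = 10% | p = 20% | p = 30% |
|---|---|---|---|
| Kept, w = 0.5 | 79.1% | 78.4% | 78.0% |
| Kept, w = 1.5 | 72.4% | 67.1% | 63.6% |
| Lost and not replaced (27, 24, 21 per arm) | 75.6% | 70.4% | 64.3% |

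At w = 0.5, losing these patients costs more power than keeping them; at w = 1.5 the order reverses. The documents cannot say which applies.

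**The case against.** The best defence is that the clause is permissive, nobody is told to stop, and general safeguards exist. These include parental signature, ethics and Ministry approval, illness education, thorough answers to questions, frequent visits and a sickle cell service next door. The consent pages were removed and the appendices not supplied, so warnings, a clinician contact or a medication item may be there. All of this stands and limits the claim to the supplied text. It does not close the gap, because none of the visible safeguards addresses stopping or restarting hydroxyurea, and eligibility rules and review triggers belong in the protocol body.

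A reader might infer three stronger things, and the documents support none of them:

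- **That patients will be harmed.** The only basis is the remark in 3e about what the drug does. Nothing describes the effect of up to 12 weeks without it, or says that any user is expected to enrol. The point is precautionary.
- **That the treatment comparison is biased, or that it is safe from bias.** Stopping before randomisation does not itself favour an arm. But abstinence must continue after open-label randomisation, so resumption could differ between arms. Neither conclusion can be asserted.
- **That the clause should change for the sake of power.** The second table shows that the sign of that argument depends on an unsupported assumption.

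Barring everyone who has ever stopped the drug would also go further than the defect requires, given the plan's stated wish to keep exclusions few.

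**Conclusion.** The point holds as a patient-safety gap in the eligibility rule. Following 3e as written, a hydroxyurea user aged 13 or over can enter by stopping a drug that the plan says counters the disease. The supplied text requires no treating-clinician agreement, sets no time off drug and gives no restart rule, and its review triggers look only at the wound. This should be fixed.

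The number affected is unknown and may be zero; the exposure table rests wholly on assumed shares. The conclusion also assumes that the unseen consent pages and appendix forms do not already cover the matter.

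The statistical consequence is secondary and cannot be sized. Differential resumption could affect the intention-to-treat comparison. It could also affect the per-protocol non-inferiority fallback in section 3a, which does not say whether a patient who resumes still counts as having completed treatment.

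**What to change.** **Section 3e.** Delete the clause that lets a user abstain, so that nobody stops the drug in order to enter. At minimum, replace it with: eligible only if the treating sickle cell clinician documents agreement, with a time off drug before baseline set in advance by the sickle cell clinicians. The documents give no figure for that period. Deletion is preferable, because the minimum version still leaves abstaining patients under wound-only review triggers. Patients already off the drug for reasons unrelated to the trial remain eligible after the same period.

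**Resumption.** State that resuming on clinical advice is always allowed, and that patients who resume stay in the intention-to-treat analysis.

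**Section 3d.** Record hydroxyurea history at baseline (never, or stopped with date of last dose) and current use weekly (yes/no). Report both by arm, for the per-protocol set as well.

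**Cost.** One baseline item, one weekly item, and the possible loss of would-be abstainers from recruitment. If other patients fill the 120 places there is no loss of numbers. The loss matters if many would have abstained and the enrolment window, which "will close 60 days later, or when a maximum of 120 patients have enrolled", ends first.
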